8.0 Study Withdrawal/Discontinuation

Subjects may be withdrawn from study participation at the discretion of the investigator or if the patient/surrogate or attending physician requests that the subject be withdrawn. The reason and date of every withdrawal will be recorded. The Informed Consent Document will notify participants that their participation is voluntary, and they can tell the study staff at any time if they decide to stop participating. In addition, if they choose to withdraw their authorization for study staff to access protected health information (PHI) in the medical record, they may do so by notifying study staff in writing. If a participant chooses to no longer participate but does not notify study staff that they withdraw authorization for access to PHI, their medical record may be accessed to obtain outcomes and safety data. Follow-up will be performed for all discontinuations due to an AE or other safety concern until resolution, until deemed chronic and stable, or as long as clinically appropriate.

Definitions:

Pancreatic fistulae will be defined by pre-existing definitions in the literature.

In general, a pancreatic fistula is considered to be leak from the pancreatic ductal system. More specifically, it is formally defined as an abnormal connection between pancreatic epithelium with another epithelial surface containing pancreatic fluid. In the context of pancreatic surgery where a pancreateojejunal anastomosis is created and a surgical drain is utilized, a fistula likely indicates a failure of proper healing of the anastomosis and may not be connected to another epithelial surface but instead a drain [7].

We will define a pancreatic fistula as output of at least 10mL/day of amylase-rich fluid (amylase content greater than 3 times the upper normal serum value) for greater than 5 days. Accordingly, drains placed near the pancreateojejunostomy will have daily outputs and daily amylase levels checked on the first five days following surgery.

Additionally, pancreatic fistulae are grading based on severity and will be classified as either grade A, grade B, or grade C as defined by the International Study Group on Pancreatic Fistula.

- Grade A pancreatic fistulae are the most common and have limited to no clinical impact. The patient appears clinically well, there are no signs of infection or sepsis, there is typically no evidence of a fluid collection, drainage resolves and no specific treatment is indicated.
- In contrast grade B fistulae require a change in clinical management; patients are made NPO (nothing by mouth) and supported with enteral or parenteral nutrition. They require leaving pancreatic drains in place and will often necessitate a delay in discharge.
- In patients with a grade C fistula, major deviations in management are required. These patients may not be clinically stable and require aggressive interventions including care in the intensive care, nothing by mouth, supplemental nutrition, intravenous antibiotics and percutaneous drainage with a possible return trip to the operating room for repair, creation of a new

anastomosis between the pancreas and the gastrointestinal tract, or completion pancreatectomy [7].

Superficial and organ space infections are defined as follows from pre-existing definitions in the literature [6]:

Superficial infections will be defined as an infection which occurs within 30 days after surgery and involves either skin/subcutaneous tissue (superficial) or the fascial/muscle layer (deep) of the incision. Furthermore, the patient will need to meet at least one of the following criteria:

1. Purulent drainage from the incision but not from the organ/space component of the surgical site;
2. Organisms isolated from an aseptically obtained culture of fluid or tissue from the superficial incision;
3. At least one of the signs or symptoms of infection, including pain or tenderness, localized swelling, redness and heat and a superficial incision deliberately opened by a surgeon and either found to be culture-positive or not cultured (a culture-negative finding did not meet this criterion);
4. A deep incision spontaneously dehisced or deliberately opened by a surgeon and either found to be culture-positive or not cultured (a culture-negative finding did not meet this criterion) and at least one of the signs or symptoms of fever ($>38^{\circ}\text{C}$), localized pain or tenderness;
5. An abscess or other evidence of infection involving the deep incision found on direct examination, during reoperation, or by histopathologic or radiologic examination.

Organ space infections will be defined as infections that occur within 30 days after surgery that is related to the surgery and involves any part of the body excluding that skin, fascia, or muscle layers, and meets at least one of the following criteria:

1. Purulent drainage from a drain that was placed through a stab wound into the organ or space;
2. Organisms isolated from an aseptically obtained culture of fluid or tissue in the organ or space;
3. An abscess or other evidence of infection involving the organ or space found on direct examination, during reoperation, or by histopathologic or radiologic examination.
4. Any intraperitoneal collection requiring percutaneous drainage

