2.0 Rationale and Specific Aims

Antibiotic irrigation during abdominal surgery via peritoneal lavage is used commonly in abdominal surgery when there are concerns about contamination. This technique offers the ability to decrease bacterial load, thereby potentially reducing intra-abdominal infections. While irrigation typically consists of normal saline, several antibiotics have been used with varying degrees of success. Recent literature in the field of colorectal surgery has demonstrated that the intraoperative use of antibiotic irrigation decreases wound complication rates to less than 5% compared to a rate of 14% among those receiving normal saline irrigation [5].

Hypothesis: The routine use of intraoperative antibiotic irrigation during pancreatoduodenectomy will decrease superficial and organ space infections.

Primary Specific Aim:

- Test the efficacy of routine antibiotic irrigation in reducing superficial and organ space infections among patients undergoing pancreatoduodenectomy.

Secondary Specific Aim:

- Test the efficacy of antibiotic irrigation in reducing pancreatic fistula rates.

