The patient, treating surgeon, and research nurse coordinator will be blinded to the assigned treatment during the course of the study. Upon randomization, the investigational pharmacy will prepare two one liter bags of normal saline solution, either with the antibiotic or just normal saline. During the procedure, the solution will be provided and documentation of the treatment administered will be made as part of the investigational pharmacy documentation.

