9.0 Statistical Considerations

The patients' characteristics will be summarized by treatment arms and compared using two-sample t-tests for continuous and Chi-square test for categorical variables as appropriate. Nonparametric tests will be used if there is a normal distribution assumption violation. All analysis will be performed using SAS 9.3 (Cary, NC)

Efficacy in reducing superficial and organ space infections. In the primary analysis, proportion of patients with infection will be tabled and calculated for each arms and compared using a Chi-square test. In the secondary analysis, we will also use a logistic regression model with infection as the outcome variable, treatment arm as the main predictor, and will adjust for disease process in order to further evaluate the efficacy.

Efficacy in reducing pancreatic fistula rates will be analyzed in a similar way to the primary outcome variable.

Toxicity data related to the treatment will be summarized by treatment arm.

Early Stopping Rule:

An interim analysis will occur after 82 patients have been treated. Overall complication rate and rate of major complication (e.g. Grade 3 through 5) will be analyzed for each treatment group at the interim analysis. If the placebo group infection rate is three (3) times the infection rate of the treatment group, the study will be stopped.

Sample Size and Statistical power: Historical data in hepatopancreatobiliary surgery show that the treated group will reduce primary outcome rate from 24% to 8%. The anticipated reduction in infectious complications was estimated based on historical outcome data for abdominal operations involving one or more gastrointestinal anastomoses. Using a two-sided Chi-square test, we will need 82 patients in each arm to detect such a difference with 80% power and 5% Type I error rate. With no attrition rate, we will need to recruit 164 patients totally. The power analysis was performed for the primary endpoint only.

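### The scheduled drain readings end on day 5, so on their own they cannot show that the fistula definition's duration of more than 5 days has been met

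*Combined protocol and SAP*

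**What the plan says.** Section 2.0 gives one secondary aim: "Test the efficacy of antibiotic irrigation in reducing pancreatic fistula rates". Section 9.0 adds: "Efficacy in reducing pancreatic fistula rates will be analyzed in a similar way to the primary outcome variable". That means a chi-square comparison of proportions, followed by a logistic regression adjusted for disease process.

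The endpoint is defined in section 8.0, under Definitions. The text opens with a general reference, "Pancreatic fistulae will be defined by pre-existing definitions in the literature", and then states the trial's own rule: at least 10 mL/day of drain fluid with "amylase content greater than 3 times the upper normal serum value) for greater than 5 days". The following sentence is worded as a consequence of that rule. It requires drains near the anastomosis to have "daily outputs and daily amylase levels checked on the first five days following surgery".

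The same section then describes three severity grades. On the mildest it says "Grade A pancreatic fistulae are the most common and have limited to no clinical impact", and that no specific treatment is indicated. On grade B it says "They require leaving pancreatic drains in place and will often necessitate a delay in discharge".

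**The concern.** The duration clause and the measurement schedule are adjacent, and the second is meant to serve the first, yet the schedule ends before the duration can be reached. Nothing else in the plan requires a drain output or amylase reading after day 5.

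At stake is whether the only secondary endpoint can be classified in the same way for every patient. A patient with qualifying output on all five days has no defined status. One assessor could call this a fistula because everything measured was positive. Another could call it no fistula because the stated duration was never shown. A patient whose drain is out before a sixth reading raises the same problem, and no rule covers either case.

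**Working it through.** **Inputs, all from section 8.0 unless stated**
- Volume: at least 10 mL/day.
- Amylase: above 3 times the upper normal serum value.
- Duration: more than 5 days.
- Scheduled readings: daily on the first five days after surgery.
- Patients: 82 per arm, 164 in total (section 9.0).

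**Step 1. Readings needed against readings scheduled.** With one reading per day, more than 5 days needs at least 5 + 1 = 6 qualifying days. The schedule supplies at most 5. The shortfall is at least 6 − 5 = 1 day.

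**Step 2. What the five readings can and cannot decide.**
- All five qualify: the duration is 5 days so far, so the criterion is neither met nor excluded.
- At least one does not qualify: a run continuous from day 1 is excluded. A run that begins later is not. The plan does not say that the days must start on day 1 or be consecutive.
- No pattern of five readings reaches 6 qualifying days.

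**Step 3. How far past day 5 readings would have to go.** For a consecutive run starting on day k, the sixth day is day k + 5. For k = 1 the sixth day is day 6, one reading beyond the schedule. For k = 5 it is day 10, five readings beyond it.

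**Step 4. Other places where the missing information might be required.**
- Section 6.0 (Study Calendar): no drain or amylase row. It also omits the day 1 to 5 readings that section 8.0 does require, so its silence is weak evidence about later readings.
- Section 7.0 (Adverse Event Reporting): adverse events are recorded until 30 days after surgery whether or not related. This could capture a fistula that is recognised clinically, but it requires no drain amylase.
- Section 8.0, grade descriptions: grade B mentions drains left in place but sets no measurement.
- Section 8.0, withdrawal text: permits use of the medical record for participants who stop taking part. It does not say what that record must contain.

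**Step 5. Does this reach the primary endpoint?** The plan's sample size for infection, 24% against 8%, reproduces. With the pooled formula, n = [1.96·√(2·0.16·0.84) + 0.8416·√(0.24·0.76 + 0.08·0.92)]² / 0.16² = (1.0162 + 0.4258)² / 0.0256 ≈ 81.2, rounded up to 82 per arm. Fistula status does not enter this calculation, and section 9.0 powers the primary endpoint only.

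**The case against.** The strongest reply is that the plan defers to published definitions, so the duration wording or the five-day schedule may be a drafting slip that the cited source would resolve. That may be so. The content of that source is not in the documents, however, and the rule the trial states as its own is the one with the longer duration. If the source settles the matter, one of the two sentences still has to change.

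A second reply is that fistulae will be found anyway. Drains may be read clinically after day 5, adverse events are recorded to 30 days, and grade B and C fistulae change management and so leave a record. This stands, and it limits the point. A reader might infer that no fistula can be recorded in the trial, or that the endpoint is unusable. The documents do not support that. The gap falls mainly on grade A and borderline cases, which leave little management record.

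A reader might also infer a definite loss of cases and of power. Being the most common of three grades puts grade A above one third of fistulae, but that is not the share missed, because some grade A patients will have later readings. As an illustration only, take assumed true rates of 20% against 10% with 82 per arm and equal under-detection in both arms. Power is then 43% with none missed, 39% with 10% missed and 29% with one third missed. Neither the rates nor the missed shares are in the documents. The calculation also ignores the opposite error, in which patients positive on all five days are counted as fistulae without proof of duration.

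Nor do the documents support an inference of bias toward one arm: "The patient, treating surgeon, and research nurse coordinator will be blinded to the assigned treatment during the course of the study".

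**Conclusion.** The point holds in this form. The scheduled readings are at least one day short of the stated duration, so they cannot by themselves establish that the criterion is met, whatever they show. Confirmation depends on data that no section requires.

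The shortfall of 5 readings against 6 follows from the text and needs no assumption beyond one reading per day. That the gap falls mainly on grade A and borderline cases is a judgement based on the plan's own grade descriptions. With blinding as described, the error should be mainly non-differential. Its direction is unknown, and its effect on the fistula rate or on power cannot be derived from the documents.

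The infection endpoint and its 82 patients per arm are untouched. This should be fixed, but it does not threaten the trial's main conclusion.

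**What to change.** Reconcile the duration clause and the reading schedule in section 8.0. The sponsor must decide which sentence reflects the intent, by one of two routes:

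- **Restate the classification rule.** Before unblinding, reword it so that fistula status can be decided from the five scheduled days, and check the wording against the definition the protocol cites. This costs no extra testing. The reported rate may then no longer be a strict rate for more than 5 days, and shorter-lived output may count.
- **Extend the readings.** State that output and amylase readings continue past day 5 while a drain remains in place. This costs at most 164 readings per added day if every patient still has a drain, and fewer otherwise. By step 3, one to five added days cover runs starting on days 1 to 5. It helps only patients not yet operated on; those already treated would have whatever their charts contain.

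Under either route, write down before unblinding how to classify patients who are positive on all five days and patients whose drain is out before the criterion can be assessed. Report the number undetermined in each arm. This needs no new data.

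Nothing is proposed about when drains are removed.

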9.0 Statistical Considerations

The patients' characteristics will be summarized by treatment arms and compared using two-sample t-tests for continuous and Chi-square test for categorical variables as appropriate. Nonparametric tests will be used if there is a normal distribution assumption violation. All analysis will be performed using SAS 9.3 (Cary, NC)

Efficacy in reducing superficial and organ space infections. In the primary analysis, proportion of patients with infection will be tabled and calculated for each arms and compared using a Chi-square test. In the secondary analysis, we will also use a logistic regression model with infection as the outcome variable, treatment arm as the main predictor, and will adjust for disease process in order to further evaluate the efficacy.

Efficacy in reducing pancreatic fistula rates will be analyzed in a similar way to the primary outcome variable.

Toxicity data related to the treatment will be summarized by treatment arm.

Early Stopping Rule:

An interim analysis will occur after 82 patients have been treated. Overall complication rate and rate of major complication (e.g. Grade 3 through 5) will be analyzed for each treatment group at the interim analysis. If the placebo group infection rate is three (3) times the infection rate of the treatment group, the study will be stopped.

Sample Size and Statistical power: Historical data in hepatopancreatobiliary surgery show that the treated group will reduce primary outcome rate from 24% to 8%. The anticipated reduction in infectious complications was estimated based on historical outcome data for abdominal operations involving one or more gastrointestinal anastomoses. Using a two-sided Chi-square test, we will need 82 patients in each arm to detect such a difference with 80% power and 5% Type I error rate. With no attrition rate, we will need to recruit 164 patients totally. The power analysis was performed for the primary endpoint only.

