6.0 Study Calendar

	Baseline	Surgery	Follow up	
	(-30 days-Day 0)	Day 0	Day 30 (+/- 14 days)	Day 90 (+/-14 days) [Telephone Visit]
REQUIRED ASSESSMENTS				
Medical history	x			
Height, Wt	x		x	
Physical examination	x		x	
Vital Signs	x		x	
AE and concomitant medication assessment	x	x	x	
Survival				x
TREATMENT				
Randomization	x*			
Polymyxin B/Placebo Irrigation		x		

x* randomization occurs after patient is registered to the study, prior to surgery

Toxicities to be monitored in this study:

Any evidence of allergic reaction to the antibiotic irrigation will be considered an adverse event.

7.0 Reporting of Adverse Events or Unanticipated Problems involving Risk to Participants or Others

Definitions of Adverse Events

Adverse Event (AE)

An **adverse event** is defined as untoward medical occurrence associated with the use of a drug or procedure in humans, whether or not considered drug or procedure related. An adverse event can be **ANY** unfavorable and unintended sign, symptom, or disease temporarily associated with the use of a medicinal (investigational) product or procedure, whether or not considered related to the medicinal (investigational) product or procedure (attribution of ‘unrelated’, ‘unlikely’, ‘possible’, ‘probable’, or ‘definite’). Examples of Adverse Events that will be recorded in this study are:

- Concomitant illness
- Physical injury
- Events possibly related to medication
- Significant worsening (change in nature, severity, or frequency) of the disease under study or other pre-existing conditions

- Drug interactions
- A laboratory or diagnostic test abnormality occurring shortly after the start of the study that results in the withdrawal of the patient from the study, requires medical treatment or further diagnostic work-up, or is considered by the study investigator to be clinically significant

Adverse events will be graded according to the NCI Common Toxicity Criteria, Version 4.0. Delayed gastric emptying will be graded using the International Study Group of Pancreatic Surgery (ISGPS) system.

Serious Adverse Event (SAE)

A serious adverse event is any untoward medical occurrence resulting in one or more of the following:

- Results in death or ANY death occurring within 28 days of last dose of study drug (even if it is not felt to be drug related)

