- Is life-threatening (defined as an event in which the patient was at risk of death at the time of the event; it does not refer to an event which hypothetically might have caused death if it were more severe)
- Requires inpatient hospitalization or prolongation of existing hospitalization

NOTE: Hospitalizations that are not considered SAEs are:

- Hospitalization planned prior to first administration of study drug
- Hospitalization for elective treatment of a pre-existing condition unrelated to the study medication

- Results in persistent or significant disability/incapacity
- Is a congenital anomaly or birth defect
- Is an important medical event (defined as a medical event(s) that may not be immediately life-threatening or result in death or hospitalization but, based upon appropriate medical and scientific judgment, may jeopardize the patient or may require intervention (e.g., medical, surgical) to prevent one of the other serious outcomes listed in the definition above). Examples of such events include, but are not limited to, intensive treatment in an emergency room or at home for allergic bronchospasm; blood dyscrasias or convulsions not resulting in hospitalization; or the development of drug dependency or drug abuse.

Unexpected Adverse Event

An adverse event not mentioned in the package insert or the specificity or severity of which is not consistent with the package insert.

Determining Attribution to the Investigational Agent(s)

Attribution: An assessment of the relationship between the AE and the medical intervention. CTCAE does not define an AE as necessarily *“caused by a therapeutic intervention”*. After naming and grading the event, the clinical investigator must assign an attribution to the AE using the following attribution categories:

Relationship	Attribution	Description
Unrelated to investigational agent/intervention	Unrelated	The AE is clearly NOT related
	Unlikely	The AE is doubtfully related
Related to investigational agent/intervention	Possible	The AE may be related
	Probable	The AE is likely related
	Definite	The AE is clearly related

Adverse Event (AE) Reporting

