Adverse events (AEs) will be reported to the principal investigator immediately and will be recorded from the time of first study drug administration until 30 days after surgery, regardless of whether or not the event(s) are considered related to trial procedures or medications. All AEs considered related to trial medication will be followed until resolution, return to baseline, or deemed clinically insignificant, even if this occurs post-trial.

Reporting to the IRB:

1. Unanticipated problems involving risks to subjects or others will be reported **promptly** to the IRB if they:
 - caused harm;
 - were unexpected;
 - were related or possibly related to the research intervention; AND
 - required revision to the informed consent document.

If the serious adverse event does not meet all four (4) criteria listed above, the event does not have to be promptly reported to the Indiana University IRB. However, it will be reported at the time of continuing review.

2. **Prompt** reporting of unanticipated problems to the IRB is defined as within 5 days from becoming aware of the event.

Reporting to the Data Safety Monitoring Committee (DSMC):

Regardless of study sponsorship, the DSMC chair and/or coordinator will review all expedited SAE reports through OnCore®. Expedited reports are completed per IRB guidelines and may include the IRB Prompt Reporting form, non-compliance form. When follow-up information is received, a follow up report will also be created in OnCore. The DSMC chair and/or coordinator will review expedited SAE reports monthly, and report findings to the DSMC.

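### The only final safety summary in Section 9.0 is worded around treatment-related toxicity, and no final by-arm summary of all adverse events, Grade 3-5 events, SAEs or deaths is named

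*Combined protocol and SAP*

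**What the plan says.** The final safety analysis in Section 9.0 is a single sentence: "Toxicity data related to the treatment will be summarized by treatment arm". The only other by-arm safety analysis in that section is under Early Stopping Rule: "Overall complication rate and rate of major complication (e.g. Grade 3 through 5) will be analyzed for each treatment group at the interim analysis". The interim takes place once 82 patients have been treated; the planned total is 164.

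Collection is wider than this. Section 7.0, under Adverse Event (AE) Reporting, has events recorded from the first study irrigation to Day 30 "regardless of whether or not the event(s) are considered related to trial procedures or medications". The same section grades them with the NCI criteria, grades delayed gastric emptying separately, and counts any death within 28 days of the last dose as serious even if it is not thought to be drug related. The Study Calendar (Section 6.0) marks survival at a telephone contact around Day 90.

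Two clinical outcomes are compared at the end regardless of attribution. Infection is the primary outcome, and for fistula Section 9.0 says "Efficacy in reducing pancreatic fistula rates will be analyzed in a similar way to the primary outcome variable".

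**The concern.** In this protocol, related is a working category. A statistician who follows the final safety sentence literally could tabulate only events that the investigator judged possibly, probably or definitely related, and still comply with the plan. Events judged unlikely or unrelated would have been recorded and graded but would have no planned place in the final comparison of arms.

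After major surgery, attributing a single complication to the irrigation or to the operation is a matter of judgement. A randomised comparison of all events does not need that judgement, and this is the information that the plan does not commit to producing. At stake are complications other than infection and fistula (delayed gastric emptying is one that the protocol grades), SAEs, and deaths.

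**Working it through.** The plan's one relevant calculation is the sample size, and it reproduces. With 24% versus 8%, a mean rate of 16%, two-sided 5% and 80% power:

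n per arm = [1.96 × √(2 × 0.16 × 0.84) + 0.8416 × √(0.24 × 0.76 + 0.08 × 0.92)]² / 0.16² = (1.0162 + 0.4258)² / 0.0256 = 81.2, rounded up to 82, or 164 in total.

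The concern does not depend on this figure, and extra safety tables would not change it. The check itself is a reading of the text.

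1. **What related means.** The attribution table in Section 7.0 places Possible, Probable and Definite under related, and Unlikely and Unrelated under unrelated; the last is described as "The AE is clearly NOT related". The AE reporting text then uses the related group as a subset: "All AEs considered related to trial medication will be followed until resolution".

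2. **Three readings of the final safety sentence.**
   - *Middle:* events classed as related in the attribution table. This matches the protocol's own use of the word and is the most natural reading.
   - *Looser:* all toxicity data from the treated patients, whatever the attribution.
   - *Narrower:* the toxicities listed for monitoring under the Study Calendar, where the only entry is "Any evidence of allergic reaction to the antibiotic irrigation will be considered an adverse event".

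3. **What each reading leaves without a named final by-arm summary.**

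| Item collected | Looser | Middle | Narrower |
|---|---|---|---|
| AEs to Day 30 judged related | covered | covered | allergic reactions only |
| AEs to Day 30 judged unlikely or unrelated | covered | not covered | not covered |
| Grade 3-5 events and SAEs as separate rows | not named | not named | not named |
| Deaths after Day 30 | not named | not named | not named |

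The last row follows from the time windows. The irrigation is given only at surgery, so the 28-day death rule and AE recording have both ended by Day 30. A later death reaches the dataset as survival status at the Day 90 call, and Section 9.0 does not mention survival.

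4. **Other places where a final summary might be.** The interim analysis covers overall and Grade 3-5 complications by group, but at 82/164 = 50% of the patients. The Data Safety Monitoring Plan provides for monthly summaries and monthly review of deaths; neither is stated to be by arm, and both are oversight during the trial. I found no final by-arm safety table elsewhere in the document.

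5. **Size.** The number of events that a related-only table would omit equals the number of events times the share judged unlikely or unrelated. The documents give no attribution shares, so this cannot be computed.

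**The case against.** The strongest reply is that the sentence is ambiguous. Section 9.0 does not refer to the attribution table, all adverse events are graded with criteria that carry toxicity in their name, and the monitoring plan speaks of significant toxicities without an attribution filter. On the looser reading, the recorded events are already summarised by arm and only table-shell detail is missing. This stands in part: a reader might infer that the plan definitely excludes unrelated events, and the text does not support that certainty. But three defensible readings of the only final safety sentence are a reason to reword it, and even the looser reading does not reach deaths after Day 30.

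A second reply is that the main harms are compared anyway. That is largely true for infection and fistula, and the infection definition also takes in abdominal collections that need a percutaneous drain. The gap is confined to what remains.

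A third is that the table can still be produced later, since the data are kept. It can, but nothing commits the sponsor to it.

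A reader might also try to size the loss from precision. With 40% morbidity in both arms, the 95% half-width for the difference, 1.96 × √(2 × 0.4 × 0.6/n), is 21.2 points at 41 per arm (assuming equal allocation at the interim) and 15.0 at 82. The arithmetic is right, but it only compares half the sample with all of it. The 40% in the Background includes infections and fistulae, which are compared at the end in any case. The mortality ceiling of 5% has no time window, so expected deaths by Day 30 or Day 90 cannot be derived from it. Neither figure measures what the sentence omits.

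**Conclusion.** The point holds as a limited gap in the planned final safety analysis. It rests on reading related as Section 7.0 uses it, which is the most natural reading but not the only one. The absence of a named final by-arm summary of Grade 3-5 events, SAEs and deaths does not depend on that choice.

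A reader might go further and infer biased safety reporting or a threat to the efficacy result. The documents support neither. The patient, surgeon and research coordinator are blinded, so an attribution filter should not favour an arm, and the infection and fistula comparisons do not use attribution. The loss is information, of a size the documents do not allow one to state. The meaning of complication at the interim, which Section 9.0 leaves undefined, is a separate point and is not needed for this one.

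**What to change.** Replace the final safety sentence in Section 9.0 with:

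> All adverse events recorded to Day 30, regardless of attribution, will be summarised by arm for all treated patients as the number and proportion with any event, any Grade 3-5 event and any SAE, with events judged related shown as a subset; deaths will be summarised by arm through the Day 30 visit and the Day 90 contact, with patients of unknown status counted separately.

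The wording ties deaths to the visit and the contact because both have a window of 14 days either way. A patient seen at Day 16 or called at Day 76 may have no later scheduled confirmation of status at Day 30 or Day 90. Counting unknown status separately deals with this without new follow-up.

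The cost is one sentence and one further table from data the protocol already collects. Sample size, visits and the efficacy analysis do not change.
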